# 6.0 Interim Analyses and Safety Monitoring Analyses (if applicable)

There are no planned interim analyses or conditions for early termination / registry stoppage due to retrospective study design.

# 7.0 Analysis Specifications

SAS Analysis Dataset Specifications

- A specifications document is created following the template defined in MD146539 Work Instructions for Analysis Data Set (ADS) and MD146540 Analysis Data Set (ADS) Template for each analysis data set with at least the following details:
- Variable name
- Format
- Label
- Input variables and derivation rules

Statistical Output Specifications

- A specifications document is created in accordance with the corresponding template that contains at least the following details:
- Title and footnote
- Column headers
- Row labels for tables
- Cell formats
- Datasets and variables used with derivation details
- Revision history

Verification Level for Statistical Output

- All Analysis Datasets Level I
- All Tables Level I
- All Listings Level II

# 8.0 Data Sets, Tables, Figures, and Listings

This section includes a list of the minimal planned statistical outputs, including tables, listings and figures which are to be created for the regulatory reports defined in the protocol. A different selection of tables, listings, and figures can be created for all other reporting efforts (Annual Reports etc.) as deemed necessary.

- 8.1 Analysis Tables
  - Summary of Subject Demographics by cohort
  - Summary of Medical History by cohort
  - Summary of concomitant medication by cohort
  - Summary of procedural details and assessments by cohort
  - Summary of discharge details by cohort
  - Summary of the devices used by cohort
  - Summary of follow-up, subject availability by visit with counts and percentages.
  - Kaplan-Meier estimate of the Device-related seroma or infection through 5 years in the PAD cohort
  - Kaplan-Meier estimate of the Secondary Patency (revascularization) through 5 years in the PAD cohort
  - Kaplan-Meier estimate of Survival through 5 years in the AA cohort
  - Kaplan-Meier estimate of the Primary Patency through 5 years in the AA cohort
  - Kaplan-Meier estimate of the Device-related infection through 2 years in the DA cohort
  - Kaplan-Meier estimate of the Useable access circuit(reported as secondary patency) through 2 years in the DA cohort
  - Kaplan-Meier estimate of the Limb Salvage through 1 year in the PAD cohort
  - Kaplan-Meier estimate of the Amputation-free survival through 1 year in the PAD cohort
  - Kaplan-Meier estimate of the Device-related Adverse Events through 1 year in the PAD cohort
  - Kaplan-Meier estimate of the Device-related infection requiring reoperation through 5 year in the PAD cohort
  - Kaplan-Meier estimate of the Primary Patency through 1 year in the PAD cohort

- Kaplan-Meier estimate of the Device-related Adverse Events through 1 year in the DA cohort
- Kaplan-Meier estimate of the Primary Patency through 1 year in the DA cohort
- Summary of the Device-related SAEs by cohort
- Summary of the Device-related death by cohort
- Summary of the procedure-related death by cohort
- Summary of the procedure-related SAE by cohort
- Summary of Repeat Interventions by cohort
- Summary of Freedom from Limb Salvage by cohort
- Summary of Device or Procedure Related Serious Adverse Events by cohort
- Summary of Adverse Events by MedDRA SOC, HLT, PT and Follow-up Interval (Number of Subjects, Number of Subjects with AEs, Number of AEs, at Procedure) by cohort
- Summary of Serious Adverse Events by MedDRA SOC, HLT, PT and Follow-up Interval (Number of Subjects, Number of Subjects with AEs, Number of AEs) by cohort
- •

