### 5.2. Informed Consent Process

For the inclusion of patients in the registry, the investigator should review all inclusion/exclusion criteria and, in the case of including patients who are alive and reachable at the site, the patient will be required to sign the Informed Consent Form (ICF) before enrolment in the registry.

As this study is retrospective and considering the nature of patient's disease, some patients may have died by the time they are included. The investigator is expected to make reasonable efforts to contact the potential patient, such as checking whether they are still alive, browsing through their clinical records, contacting available telephone numbers, or obtaining contact information from population and/or health care registers. If, after reasonable effort, the patients are found to be deceased or not reachable, the request for informed consent can be waived in accordance with national and local legislation.

If, during the course of the registry, patients who were not previously reachable come back to the clinical site for a visit, the investigator is expected to collect informed consent from those patients.

To protect patient privacy, patient-identifiable information (e.g., name, initials, complete birth date, and race) will not be collected.

The informed consent form will include emergency contact details for any concerns. The case history (i.e., source documents / subject chart) for each subject shall document that such informed consent was obtained, if this was obtained remotely or if the consent was waived. In case the consent was waived, the reason must be clearly described in the source document.

The EC approved consent form will be signed and personally dated by the subject and the person who conducted the informed consent discussion. The original signed informed consent form will be retained in the subject records. A copy of the signed informed consent document will be given to the subject for their records.

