### 5.13.1. Subject Discontinuation

Subjects will be discontinued from the registry in case of the explant of the device or renal transplantation for subjects enrolled in the AV access cohort.

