#### Subject Registry Completion

A subject has completed the registry when all expected follow-up visits have been completed and properly recorded in the EDC. Any subject who does not complete these requirements due to voluntary withdrawal, physician withdrawal, death, or any other reason will be considered a withdrawal.

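### Kaplan-Meier is planned for device infection and device-related adverse events with no censoring or competing-event rule; a default run would report at least, and usually more than, the share of patients who have the event

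*SAP*

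**What the plan says.** SAP 8.1 (Analysis Tables) names Kaplan-Meier for five safety outputs outside the aortic cohort:

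- PAD primary safety: "Kaplan-Meier estimate of the Device-related seroma or infection through 5 years in the PAD cohort".
- Dialysis primary safety: "Kaplan-Meier estimate of the Device-related infection through 2 years in the DA cohort".
- PAD secondary: "Kaplan-Meier estimate of the Device-related infection requiring reoperation through 5 year in the PAD cohort".
- PAD secondary: "Kaplan-Meier estimate of the Device-related Adverse Events through 1 year in the PAD cohort".
- Dialysis secondary: "Kaplan-Meier estimate of the Device-related Adverse Events through 1 year in the DA cohort".

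The two primary safety outcomes cover four of the five analysis populations in SAP 5.0.

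Neither document gives a censoring rule or mentions competing risks or cumulative incidence. The nearest text concerns registry status. Under Subject Registry Completion in SAP 4.0, a subject who does not finish follow-up because of "death, or any other reason will be considered a withdrawal". Protocol 5.13.1 says subjects are "discontinued from the registry in case of the explant of the device or renal transplantation", with transplantation applying only to the AV access cohort. Protocol 9.1.3 collects adverse events up to completion or discontinuation. Protocol 4.1 keeps patients who died during follow-up in the registry, and Protocol 5.12 expects no loss to follow-up.

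SAP 2.5 and 5.0, and Protocol 10.1, name a different method for all primary and secondary outcomes: a proportion with an exact binomial 95% confidence interval. SAP 5.0 drops subjects whose outcome is missing.

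**The concern.** A patient who dies cannot later have a graft infection, and an explanted graft cannot later become infected. Kaplan-Meier handles a censored patient as still at risk and represented by those who remain. If death and explant are censored, 1-KM estimates the risk in a hypothetical population where neither occurs. It does not estimate the proportion of implanted patients who had the event, which is the natural reading of a safety rate in a registry that sets out to confirm safety.

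The design makes the choice matter more. Patients who died are deliberately kept and loss to follow-up is not expected. If that holds, most censoring before the 2- or 5-year horizon would be death, explant or transplantation, with little ordinary censoring. The error runs one way: it can make a device look worse than it is, never better.

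**Working it through.** **The plan's own figure.** The documents give no infection or adverse event rate to reproduce. Their only planning figures are the sample sizes, and these reproduce. The Clopper-Pearson 95% half-width is 11.97% for n = 72 at 55% and 11.88% for n = 65 at 32%. The total is 72×2 + 65 + 72×2 = 353. The sizes rest on patency and survival, so this point does not affect them.

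**Direction.** Let S(t) be Kaplan-Meier for the event with competing events censored, and G(t) the overall probability of being free of both kinds of event. Each new event adds S × hazard to 1-KM but only G × hazard to the cumulative incidence. G never exceeds S, so 1-KM is never below the cumulative incidence, whatever the shape of the hazards.

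**Size.** The competing proportion c is assumed, because the documents give none. It is the probability of a competing event by the horizon if the safety event did not occur. With constant hazards over the horizon:

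- a = −ln(1 − KM risk) and b = −ln(1 − c)
- actual risk = a/(a+b) × [1 − exp(−(a+b))]

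For a KM risk of 10%, a = 0.1054:

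| c | b | a/(a+b) | 1 − exp(−(a+b)) | actual risk |
|---|---|---|---|---|
| 10% | 0.1054 | 0.500 | 0.19 | 9.5% |
| 20% | 0.2231 | 0.321 | 0.28 | 9.0% |
| 30% | 0.3567 | 0.228 | 0.37 | 8.4% |
| 50% | 0.6931 | 0.132 | 0.55 | 7.3% |

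For a KM risk of 20%, the actual risk is 16.9% at c = 30% and 14.6% at c = 50%.

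In the other direction, a true 10% appears as a 1-KM of 11.8% at c = 30% and 12.7% at c = 40%. A simulation at n = 72 with c = 40% gave a mean 1-KM of 12.7% against a true 10.0%.

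**If infections occur early.** Suppose all of them fall in the first fifth of follow-up, with competing events still spread evenly. Then b is replaced by b/5, and a 10% KM risk is an actual 9.7% at c = 30% and 9.3% at c = 50%.

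**The other named estimator.** Suppose patients who have a competing event first are called missing and dropped from the binomial denominator. Take a true 10% and c = 40%. The proportion free of both events is exp(−(0.1358 + 0.5108)) = 0.524. The reported rate becomes 0.10/(0.10 + 0.524) = 16.0%, a larger error than the 12.7% from 1-KM. If those patients are counted as non-events and nothing else is censored, the proportion is events/n, which is also the Aalen-Johansen estimate.

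**The case against.** The strongest reply has six parts.

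- **No rule is written.** A reader might infer that the SAP instructs analysts to censor death, explant and transplantation. It does not. Censoring is the default behaviour of a single-event Kaplan-Meier combined with the withdrawal and discontinuation labels. SAP 7.0 leaves derivation rules to separate specifications that are not in these documents. This stands: the defect is a named estimator with no rule.
- **No rate is given.** A reader might infer heavy mortality in the PAD and dialysis cohorts. Protocol 5.2 says only that "some patients may have died by the time they are included", and inclusion comes at least 5 years (PAD) or 2 years (dialysis) after implant, so those deaths need not fall inside the follow-up window. The one survival figure, at least 33% at 5 years in SAP Table 2, belongs to the aortic cohort, which has no infection or device-related adverse event endpoint. This stands too.
- **Transplantation differs from death.** Nothing says the access graft is removed at transplantation. Observation ends, but infection is not shown to be impossible. Coding transplantation as competing could understate the risk. This changes the remedy.
- **The shift may be small beside sampling error.** At n = 72 with 7 events (9.7%), the exact 95% interval is about 4% to 19%. The 1.6-point shift at 30% competing events is well inside that. True, but more patients would narrow the interval without removing the bias.
- **The analysis is descriptive and the error is cautious.** Both are correct and they limit the consequence. They do not make the estimate describe what happened to patients.
- **Limb salvage raises the same question.** It is also planned with Kaplan-Meier, and death precludes a later amputation. It has not been sized here.

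**Conclusion.** The point holds as a missing rule attached to a named estimator. Run by default, the Kaplan-Meier outputs for infection and device-related adverse events would equal or exceed the actual risk. That direction does not depend on the hazard assumption. The size does, and it also depends on competing rates that the documents do not give. For a reported 10%, the overstatement is 0.5 points at 10% competing events, 1.0 at 20%, 1.6 at 30% and 2.7 at 50%. It falls to 0.3 and 0.7 points at 30% and 50% if infections all fall in the first fifth of follow-up. It is probably smaller for the 1-year adverse event outputs than for the 2- and 5-year infection outputs. The documents do not support saying that the bias is known to be large in these cohorts. Because SAP 2.5 and 5.0 name a different method for the same outcomes, changing SAP 8.1 alone would leave the conflict in place.

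**What to change.** 1. In SAP 8.1, replace Kaplan-Meier with the Aalen-Johansen cumulative incidence and its 95% confidence interval for PAD device-related seroma or infection, PAD infection requiring reoperation, dialysis device-related infection, and device-related adverse events in both cohorts.
2. Define death, and explant without a prior or concurrent endpoint event, as competing events. An explant done for infection follows the endpoint event and does not compete with it.
3. In the dialysis cohort, treat renal transplantation as end of observation (censoring), with a sensitivity analysis that codes it as competing.
4. In SAP 2.5, 5.0 and 8.1, state which estimator is primary. State also that event-free deaths are not missing outcomes and stay in the exact binomial denominator.
5. Keep 1-KM as supportive output.

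The cost is SAP wording and a standard software option, with no change to data collection or sample size. The downside is less direct comparison with published Kaplan-Meier figures, which the supportive output partly offsets.

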#### 8.2 Analysis Listings

- Listing of Completion/Discontinuation Details
- Listing of Adverse Events
- Listing of Deaths

